11 REPORT OF ADVERSE EVENTS

All adverse events shown in patients during the time they are in the study will be recorded in the Data Collection Notebook, specifying:

- Type of reaction
 - Intensity: mild (no limitation of daily living activities, patient may have mild discomfort), moderate (cause some limitation of daily living activities, patient may experience increased discomfort), severe (inability to perform daily living activities; patient may report intolerable pain or discomfort).
 - Length
 - Causality with treatment and with QEEG scans: definitive, likely, possible, unlikely, unrelated, unknown.
 - Therapy administered
 - Resolution
-

For any serious adverse reaction (see box below), the physician should complete a specific form (Attachment 6) with all available data and report it immediately (if possible within a maximum period of 24 hours) by fax, telephone or e-mail to the sponsor, who will implement the corresponding Pharmacovigilance procedures in accordance with current legislation:

[name]
International Medical Director de PronokalGroup®
[name]
[name]
[contact]
[contact] or [contact].

SERIOUS ADVERSE REACTION: is any adverse reaction that can be classified in one or more of the following categories:

- Mortal
- Life threatening
- It causes significant or persistent discapacity/ disability
- It causes hospitalization or prolongs hospitalization

Congenital anomalies/birth defects and serious adverse clinical consequences associated with use under conditions other than those set out in the Summary of Product Characteristics (SPC), overdose or abuse are also included.

Medical judgment should be applied when deciding whether an event or reaction is serious in other situations. Major adverse reactions or events that do not pose immediate threat to life, or do not cause death or hospitalization but may endanger the patient, should be deemed serious.

12 ETHICAL ISSUES

12.1 General considerations

This study will be conducted in accordance with current regulations, international accepted ethical standards of Good Clinical Practice (CPMP/ICH/135/95) and the principles provided in the latest version of the Declaration of Helsinki.

12.2 Evaluation by an Authorized Clinical Research Ethics Committee

Prior to its inception, this study will be submitted to the Ethics Committee of the IEDE - Instituto Estadual de Diabetes e Endocrinologia

to obtain their approval.

12.3 Patient information and informed consent

The patient will be informed about the study issues for their knowledge and written informed consent will be requested for participation in the study.

12.4 Data confidentiality

The patient's identity will appear coded in the study forms. The clinical investigator of the clinical trial will maintain a separate confidential record listing the patient identification codes and patient record number. The data of the subjects participating in the study will be saved in an automated file, property of Protein Supplies S.L .

13 PRACTICAL CONSIDERATIONS

13.1 Workplan

The investigators will be in charge of recruiting patients. Once the patients have confirmed their willingness to participate in the study, the investigator should verify if they meet the inclusion/exclusion criteria of this study. If they are eligible, they will be requested the additional tests (blood test with liver function) and will be informed on every issue of the study through the Patient Information Sheet (Attachment 1).

At the baseline visit, once the complementary tests have been reviewed and verified to meet inclusion criteria, the physician must confirm that the patient agrees to participate in the study and obtain the patient's signature of the Informed Consent (Attachment 2). Upon signing, the investigator will verify the assigned group according to the randomization list.

At this baseline visit, the physician should request MRI and MR Elastography to assess the degree of hepatic steatosis, the amount of visceral fat and liver stiffness. The physician will also perform the first salivary cortisol test on the patient. Also, he should record the clinical data requested in the Data Collection Notebook and schedule the treatment.

During the weight loss treatment, patients in the study group will be monitored by the investigator fortnightly during the protein diet (Ketogenic Active Stage), although at these additional visits no data are expected to be collected for the study. Upon completion of the first two months of follow-up, the study group will end the ketogenic stage and from that moment on, the patients will be controlled outside the center by dietitians specialized in the Pronokal® Method. Patients in the control group (hypocaloric diet) will undergo controls at the center monthly, although data will only be recorded in the visits arranged in this protocol (screening, baseline, month2 and month 6).

At the moment the patient completes the two months of follow-up, the data requested in the DCN will be recorded, the salivary cortisol test will be performed and an MRI and a MR Elastography will be requested.

The investigator, apart from monthly visits or any additional visits deemed necessary, will have an appointment with the patient at month 6 of treatment for a new clinical assessment, will record the anthropometric data, and request a Control MRI and MR Elastography.

At the end of the 6-month follow-up, the study will be completed.

In case of drop out or discontinuation of the study, the investigator will submit the DCN visit sheets and complete the study completion sheet, specifying the reason for discontinuation.

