8 TREATMENT DESCRIPTION

8.1 Weight Loss Program: PronoKal® Method

All patients in the study group will undergo the same standardized weight loss program (PronoKal® Method) with progressive diet based on commercial high-biological-value protein preparations, dietary supplements, physical exercise plan and emotional support, structured in 3 stages: active stage, food re-education stage and maintenance stage

80% of target weight loss			20% of target weight loss		Long-term maintenance of weight loss
Multidisciplinary team (Dietary counseling/physical activity/psychological support)					
Weight Loss Moment					My New Lifestyle Moment
Step 1	Step 2	Step 3	Step 4	Step 5	
Low-fat ketogenic diet (very low-calorie-ketogenic diet) 600-730 kcal/day			Low calorie diet (800-1500 kcal/day)		Controlled diet adapted
Supplementation Vitamins, trace elements OMEGA BALANCE: 700 DHA/500 EPA			Supplementation Vitamins, trace elements DHA VITA: 500 DHA/100 EPA		DHA VITA: 500 DHA/100 EPA

a) Treatment schedule

Active stage: The diet will consist of a protein diet, ie a very low-calorie ketogenic diet (VLCK diet) (between 650 and 730 kcal/day) based on PronoKal® commercial preparations and low-glycemic-index vegetables. Patients will start with 5 commercial

preparations a day. Two of them will be replaced progressively by natural proteins (meat or fish). This active stage will be maintained for 2 months.

- Phase 1: Protein diet of 600 kcal/ day (with 5 PronoKal® products and low-glycemic-index vegetables) + Nutritional supplements (vitamins and trace elements) + Cardiovascular physical exercise + Emotional support.
- Phase 2a: Protein diet of 680 kcal/day (with 4 PronoKal® products, a high-protein food [meat or fish] and low-glycemic-index vegetables) + Nutritional supplements (vitamins and trace elements) + Cardiovascular physical exercise + Emotional support.+ Soporte emocional.
- Phase 2b: Protein diet of 780 kcal / day (with 3 PronoKal® products, two high-protein foods [meat or fish] and low-glycemic-index vegetables) + Nutritional supplements (vitamins and trace elements) + Cardiovascular physical exercise + Emotional support.

Patients will remain in Phase 1 until they have lost 40% of the excess weight or the target weight to be lost. Subsequently, they go on to Phase 2a until they have lost 60% of the excess weight and then to Phase 2b until they have lost 80% of the excess weight.

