9.2 Study procedures

9.2.1 *Follow-up of patients*

The patient follow-up will be 6 months. The patients will be visited monthly and data will be recorded on 4 occasions: pre-inclusion, baseline visit, final visit Active stage (end of ketosis) and visit at month 6.

Patients will be included after verifying the inclusion and exclusion criteria and after obtaining the signed informed consent.

Screening visit (day -15). In this visit, the patient's medical history will be assessed and a complete blood test will be required to verify the inclusion/exclusion criteria: complete blood count (red blood cells, leukocytes, neutrophils, hematocrit, hemoglobin), fasting blood glucose, Hb1c, insulinemia, lipid profile (total cholesterol, c-HDL, c-LDL, triglycerides), kidney function (serum creatinine, creatinine clearance, glomerular filtration), nitrogen balance (urea, uric acid), thyroid profile (TSH, T4) and ionogram (Na, K, Cl, Ca, Mg)

The pre-inclusion blood test will also include liver function tests as the first screening of hepatic steatosis:

- GOT
- GPT
- Gamma-GT
- Bilirubin
- Albumin
- Prothrombin time
- Ferritin
- Alkaline phosphatase.

In addition, the patients will be informed about the study through the patient information sheet (Attachment 1) and they will be provided with an informed consent (Attachment 2).

At the baseline visit (day 0). The results of the additional tests (blood tests) will be verified to complete the inclusion/exclusion criteria.

Liver function data will be reviewed. Patients with one or more of the following conditions will be considered as suspicious of hepatic steatosis:

- GPT/GOT ratio over 1
- Gamma-GT and alkaline phosphatase increased twice to three times the normal levels
- High ferritin
- Normal bilirubin and albumin in the presence of any of the above changes

The informed consent will be signed and randomized. The corresponding diet will be scheduled depending on the treatment group (VLCK diet group or control group) and the physical exercise program. Patient demographics (sex, age, weight, height, comorbidities and medication) will be recorded. Anthropometric data (weight, BMI, waist circumference) will be recorded. Fat infiltration into liver and visceral fat will be scanned by MRI and hepatic stiffness will be assessed by MR Elastography. The salivary cortisol levels will also be tested.

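### No weight is kept between months 2 and 6 although patients are seen monthly, so dropout driven by late regain could be only partly corrected at month 6

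*Combined protocol and SAP*

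**What the plan says.** Section 9.2.1 sets the general rule: "The patients will be visited monthly and data will be recorded on 4 occasions". The four occasions are pre-inclusion, baseline, the end of the active stage and month 6. The flow chart in 9.2.2 has no column between month 2 and month 6.

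Section 13.1 gives the rule by arm.
- VLCK, ketogenic stage: fortnightly visits to the investigator, "although at these additional visits no data are expected to be collected for the study".
- VLCK, after month 2: "from that moment on, the patients will be controlled outside the center by dietitians specialized in the Pronokal® Method".
- Control: monthly visits at the centre, "although data will only be recorded in the visits arranged in this protocol".

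Weight loss, liver fat and visceral fat changes from baseline to month 6 are all endpoints (9.1.3). Section 7.7 accepts a baseline MRI plus either the end-of-ketosis or the month 6 MRI as a sufficient number of scans. Section 10.2 lists t tests, Mann-Whitney, Fisher's exact test and correlations, including steatosis reduction against weight loss. It names no analysis population and no method for missing data.

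**The concern.** Months 2 to 6 are when VLCK patients leave ketosis and move to a higher intake (8.1), so regain is plausible then and the month 2 visit cannot show it. Patients who regain may be the ones who stop attending. If so, those still present at month 6 have done better than the group as randomised.

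A weight taken in months 3 to 5 would carry information on that regain. Patients are seen in those months, but the plan does not keep the weight. Follow-up also differs by arm after month 2, so retention may differ and the resulting bias need not cancel in the comparison. With 20 patients per arm (7.4), each loss counts.

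**Working it through.** **Step 1. Which weights are kept** (8.1, 9.2.1, 9.2.2, 13.1).

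| Period | VLCK | Control | Weight kept? |
|---|---|---|---|
| Screening, baseline | centre | centre | yes |
| Baseline to month 2 | fortnightly, investigator | monthly, centre | no |
| Month 2 or end of ketosis | centre | centre | yes |
| Months 3, 4, 5 | dietitians outside the centre | monthly, centre | no |
| Month 6 | investigator | investigator | yes |

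The gap that matters for a patient lost after month 2 is the fourth row. It rests on the four-occasion rule and the control-arm sentence. The fortnightly VLCK visits fall before the month 2 scan.

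**Step 2. The plan's own figures.** There is none to reproduce: 7.5 gives no effect size, SD or dropout rate. Every input below is an assumption.

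**Step 3. Bias in one arm, in SD of the month 6 outcome.** Simulation with 1,000,000 draws. Month 2 result (M2), interim weight (W) and month 6 outcome (M6) are standard normal, with higher values worse. Assumed: r(M2,M6) 0.5 to 0.9; r(W,M6) 0.7 or 0.9; r(M2,W) = 0.9 × the smaller of those two; logistic dropout with intercept −1 and slope 1 per SD, which gives 30% lost. The estimated M6 mean is compared with the true mean of 0.

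If dropout follows M2, completer bias is −0.125 to −0.229, and adjusting for M2 brings it within 0.002 of zero. Interim weights are not needed.

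If dropout follows W:

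| r(M2,M6) | r(W,M6) | Completers | Using M2 | Using M2 and W |
|---|---|---|---|---|
| 0.5 | 0.7 | −0.177 | −0.123 | 0.002 |
| 0.5 | 0.9 | −0.228 | −0.176 | 0.000 |
| 0.7 | 0.7 | −0.179 | −0.070 | 0.000 |
| 0.7 | 0.9 | −0.229 | −0.124 | 0.000 |
| 0.9 | 0.7 | −0.177 | −0.035 | 0.001 |
| 0.9 | 0.9 | −0.229 | −0.046 | 0.002 |

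The share removed by month 2 data runs from 1 − 0.176/0.228 = 23% to 1 − 0.035/0.177 = 80%.

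**Step 4. Bias in one arm, in points of body weight.** Random-slope models assumed mean loss of 12% at month 2 and 14% at month 6, slope SD 1 point per month, and dropout driven by regain.
- With 19–32% lost: completers overstate loss by 1.0–1.5 points, and using month 2 leaves 1.0–1.6.
- With 18–27% lost (month 2 SD 3, noise SD 0.5): 0.5–1.2 points for completers, and 0.5–1.2 after using month 2.
- A third model, with SD of month 6 loss about 5, r(M2,M6) 0.58 and 17–38% lost: 0.6–1.2 points for completers.

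In the first two models the slope is independent of the month 2 result, so month 2 data remove almost nothing. Using months 3 to 5 leaves about 0.

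The correlations with month 6 follow from the second model's inputs. With t months after month 2, covariance = 3² + 4t, variance = 3² + t² + 0.5², and month 6 variance = 9 + 16 + 0.25 = 25.25.
- Month 2: 9/√(9.25 × 25.25) = 0.59
- Month 3: 13/√(10.25 × 25.25) = 0.81
- Month 4: 17/√(13.25 × 25.25) = 0.93
- Month 5: 21/√(18.25 × 25.25) = 0.98

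**Step 5. The between-arm difference.** In the third model, the same dropout mechanism and mean slope in both arms gave a bias of about 0. Setting the control slope to 0, against 0.5 points per month in the VLCK arm ((14 − 12)/4), gave about −0.3 points, which understates the VLCK advantage. With about 15 completers per arm, the standard error of the difference is 5 × √(2/15) = 1.8 points.

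**The case against.** A reader might infer that a patient lost after month 2 leaves nothing with which to correct month 6. The documents do not support that. Baseline and month 2 MRI, elastography, cortisol and anthropometry are kept, as are screening and month 2 bloods (9.2.1, 9.2.2), adverse events (section 11) and the reason for discontinuation (13.1).

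A reader might also link the gap to the diet-step rule, "Patients will remain in Phase 1 until they have lost 40% of the excess weight", and conclude that the protocol itself needs the missing weights. That rule applies only in the ketogenic stage, which ends within 2 months. Nothing in the documents ties a step decision to a weight in months 3 to 5. Nor is recording banned outright: the VLCK sentence states an expectation, and adverse events are recorded throughout.

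The quantitative objections are stronger.
- The figures in points are for one arm and for weight, a secondary variable. No link from interim weight to month 6 MRI has been quantified; 10.2 only plans to study the association.
- The correction to about zero is built in, because dropout was generated from the weights later used to correct it. A patient who regains and leaves before the next visit is not rescued.
- The between-arm bias in Step 5 is small beside its standard error.
- With no missing-data method in 10.2, even the month 2 data would go unused, so recording more weights alone corrects nothing.
- Imputing MRI from several auxiliary weights at 20 per arm may be unstable.

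All of this stands and lowers the weight of the point. The recording gap in months 3 to 5 remains, as does the difference in follow-up between arms that makes unequal dropout plausible.

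**Conclusion.** The point holds as a cheap improvement. The plan holds visits between months 2 and 6 and keeps no weight from them in either arm. Data already planned suffice if dropout depends on month 2 status. If it depends on later regain, they remove between almost none and about 80% of the single-arm bias under the assumptions tried.

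That single-arm bias is roughly 0.5 to 1.5 points of body weight, but it should not be read as the bias in the treatment comparison. The latter may be near zero, and becomes material only if dropout or weight trajectories differ enough by arm. The documents give no dropout rate, slope SD or correlation, so its true size is unknown. Any benefit for the two MRI primary variables is plausible but unquantified.

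**What to change.** Amend 9.2.1, 9.2.2 and 13.1 so that date and weight are recorded in the Data Collection Notebook at the monthly visits already planned, in both arms. Months 3, 4 and 5 matter most; month 1 is optional. For the VLCK arm, include transfer of weights from the dietitians.

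Reconcile the passages on who sees VLCK patients and how often. Section 9.2.1 says monthly. Section 13.1 says fortnightly in ketosis and then outside the centre, yet also mentions the investigator's monthly visits.

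In 10.2, add a repeated-measures model for weight using all visits. Add a sensitivity analysis for missing month 6 MRI values that uses the month 2 data and one interim weight, for example the last observed. A single auxiliary weight suits 20 patients per arm better than several.

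Cost: 40 × 3 = 120 date-and-weight entries, or 40 × 4 = 160 at most with month 1, plus the transfer from the dietitians. No extra visit or scan is needed.

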Control visit at month 2 or at the end of the ketogenic stage: For patients in the VLCK diet group, as soon as the patient loses 80% of the excess weight or within 2 months of treatment, just before moving to phase 3, the patient will undergo a new control. In the case of the control group, this visit will take place at month 2 of the hypocaloric diet.

The patient will undergo a new MRI and MR Elastography. The salivary cortisol levels will also be tested. Anthropometric data are recorded, the patient undergoes a complete blood test including liver function (GOT, GPT, GammaGT, bilirubin, albumin, prothrombin time, ferritin, alkaline phosphatase) and the potential occurrence of adverse effects will be recorded.

Visit at month 6 At month 6 of the study, a new control will be performed, evaluating hepatic steatosis and visceral fat using MRI and liver stiffness using MR Elastography. The salivary cortisol levels will also be tested. A complete blood test including liver function (GOT, GPT, GammaGT, bilirubin, albumin, prothrombin time, ferritin, alkaline phosphatase) will be required and the anthropometric data, the treatment phase, the blood test results and the potential occurrence of adverse effects will be recorded.

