9.2.2 Flow chart

	Pre-study	Onset	Visit at month 2 (end of ketosis)	Visit at month 6 (Final visit)
Review of inclusion and exclusion criteria.	X	X		
General blood test with liver function	X		X	X
Patient information	X			
Informed consent		X		
Comorbidities and medication		X	X	X
Anthropometric data (weight, BMI, WC)	X	X	X	X
MRI + MR Elastography		X	X	X
Salivary cortisol test		X	X	X
Adverse reactions			X	X
Drop outs and end of study			X	X

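### Section 11 asks for all adverse events, but both arms record them only at months 2 and 6, so non-serious events rest on long recall

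*Combined protocol and SAP*

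**What the plan says.** Section 11 sets the scope: "All adverse events shown in patients during the time they are in the study will be recorded in the Data Collection Notebook". For each event it asks for type, intensity, length, causality, therapy and resolution. Serious adverse reactions go to the sponsor immediately, if possible within 24 hours, without waiting for a study visit.

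The operational sections are narrower:

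- **9.2.1 Follow-up of patients:** "The patients will be visited monthly and data will be recorded on 4 occasions". These are pre-inclusion, baseline, end of the active stage and month 6. Only the month 2 and month 6 visit descriptions say that "the potential occurrence of adverse effects will be recorded".
- **9.2.2 Flow chart:** the row "Adverse reactions" is ticked at month 2 (end of ketosis) and month 6 only.
- **13.1 Workplan, VLCK arm:** the investigator sees patients fortnightly during the ketogenic stage, "although at these additional visits no data are expected to be collected for the study". After two months, "from that moment on, the patients will be controlled outside the center by dietitians specialized in the Pronokal® Method".
- **13.1 Workplan, control arm:** patients attend the center monthly, "although data will only be recorded in the visits arranged in this protocol".

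**The concern.** An investigator who hears of a non-serious event at week 4 gets opposite signals. Section 11 says to record it. The flow chart has no column for that contact, and the workplan says the visit yields no study data. A site that works from the flow chart and workplan will leave the event until month 2 or month 6 and depend on the patient remembering it, although the patient was already in front of a clinician.

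What is at stake is the completeness and detail of the non-serious event record. Intensity, length and treatment of a mild or moderate event are hard to reconstruct months later. With 20 patients per arm, a few lost events visibly change the description.

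A second issue is who sees the patients between recording points. Frequency and setting differ by arm, so the chance that an event comes to the investigator's notice may differ too. Nothing states how an event mentioned to an outside dietitian reaches the notebook or, if serious, the physician who must report it.

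**Working it through.** The plan gives no adverse-event rate or capture figure to reproduce. The check compares the sections and then illustrates what the recall windows could mean.

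**1. Recording points after baseline (9.2.1, 9.2.2, 13.1).** VLCK: 2. Control: 2. The formal schedule is equal.

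**2. Recall windows.** Baseline to month 2: 2 months. Month 2 to month 6: 6 − 2 = 4 months. Under 9.2.1 a VLCK patient who reaches 80% of the excess weight loss early has the first control visit early. For that patient the first window is shorter and the second longer; control stays at month 2.

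**3. Contacts (13.1).**

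- Months 0–2, VLCK: 60/14 = 4.3, so about 4 contacts. One roughly coincides with the data visit, leaving about 3 with no recording.
- Months 0–2, control: 60/30 = 2 contacts, 1 with no recording.
- Months 2–6, control: 4 monthly center visits, 3 with no recording.
- Months 2–6, VLCK: dietitians outside the center. However, 9.2.1 has patients visited monthly, and 13.1 also mentions monthly investigator visits without limiting them to controls. The frequency of investigator contact is therefore unsettled.

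**4. Illustration of capture.** Assume that events are spread evenly over a window of T days and that recall decays exponentially with half-life h. Mean capture is then (1 − e^(−kT))/(kT), with k = ln 2/h. The range for h, 30 to 240 days, is an assumption and not a figure from the documents. Example: for h = 30 and T = 60, kT = 1.386 and capture = (1 − 0.25)/1.386 = 0.541.

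| h (days, assumed) | T = 14 | T = 30 | T = 60 | T = 122 |
|---|---|---|---|---|
| 30 | 0.854 | 0.721 | 0.541 | 0.334 |
| 60 | 0.923 | 0.845 | 0.721 | 0.536 |
| 120 | 0.961 | 0.918 | 0.845 | 0.718 |
| 240 | 0.980 | 0.958 | 0.918 | 0.843 |

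As scheduled, capture is 54% to 92% in the first window (60 days) and 33% to 84% in the second (122 days), in both arms. With monthly recording (30 days) it would be 72% to 96%.

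**5. Between-arm ratio (VLCK/control) under different readings.**

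- Workplan followed literally, with the first control visit at month 2 in both arms: about 1 in both periods, with capture reduced in both arms.
- Section 11 followed at every investigator contact, months 0–2: 14-day against 30-day windows. The ratio is 0.854/0.721 = 1.18 (h = 30) down to 0.980/0.958 = 1.02 (h = 240).
- Months 2–6, if control events are noted monthly and the dietitians pass nothing on: 122-day against 30-day windows. The ratio is 0.334/0.721 = 0.46 up to 0.843/0.958 = 0.88.

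The direction of any imbalance therefore depends on the period and on which section a site follows.

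**The case against.** The strongest reply is that the sections do not strictly contradict each other. Section 11 fixes what is recorded, not when, so an event at week 4 can be entered at month 2 with its length. The workplan says data are not expected at the fortnightly visits; that does not forbid noting an event. Both points stand. The problem is a conflict in practice, and under-counting is a likely consequence rather than a stated one.

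Serious reactions are covered by the immediate route, so the recall concern is confined to events outside it. This also stands, except that the link from the outside dietitians to the reporting physician is not described.

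A reader might infer that the no-data sentence about the VLCK visits by itself makes ascertainment unequal. It does not: the control arm has the same restriction and the same two recording points. A reader might also infer that a planned safety comparison is biased. The documents do not support that either. Section 9.1 lists no safety endpoint and 10.2 names no between-arm adverse-event comparison; events would be described under 10.1 as notebook variables.

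Finally, recording at every existing contact would give VLCK about 4 occasions against about 2 for control in months 0–2, and so could create an imbalance. That is correct and shapes the remedy.

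The exploratory purpose and the 40 patients limit the consequences, but do not justify setting aside events heard at visits the plan already includes.

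**Conclusion.** The concern holds in a limited form. Section 11 asks for all adverse events, while the operational sections schedule recording only twice after baseline and take no study data in between. If they are followed as written, non-serious events are likely to be under-counted in both arms, with recall windows of up to about 2 and then about 4 months. The windows follow from the schedule. The size of the loss is unknown, and the capture percentages above rest wholly on the assumed recall half-lives.

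Ascertainment may differ between arms, because contact differs in frequency and setting, the VLCK end-of-ketosis visit can come early, and the study is open-label. Neither the direction nor the existence of a net difference can be established from the documents.

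**What to change.** 1. In 13.1, change both clauses to read *no data other than adverse events*, for the fortnightly VLCK visits and for the interim control visits.
2. In 9.2.1 and 9.2.2, add adverse-event recording on the same monthly schedule in both arms, using the same open question.
3. Record events reported at any other contact as well, with the source flagged, so that the arms can be compared on the common monthly schedule alone.
4. Require the outside dietitians to pass any event to the investigator, and say how. Serious events need to reach the physician in time for the immediate route in section 11.
5. Reconcile the monthly visits in 9.2.1 with the statement in 13.1 that VLCK patients are followed outside the center after month 2.

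The cost is some protocol wording, added flow-chart entries, a notebook page and a little more data entry; the plan already describes monthly contact. One limitation remains: the extra VLCK contacts in the first two months may still prompt more reporting in that arm, even at the common monthly points. Source flags make this visible but do not remove it.
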